**Rapid testing for infectious diseases.** Upon enrollment, participants will provide 3 fingerstick whole blood samples for rapid testing of HIV, HCV and syphilis. Vivent Health prevention staff are trained to perform point-of-care tests for these infections using the Alere Determine™ HIV-1/2 Ag/AB Combo (Alere Inc., Waltham, MA); the OraQuick® HCV Rapid Antibody Test (OraSure Technologies, Bethlehem, PA); and the Syphilis Health Check™ (Trinity Biotech, Bray, Co Wicklow, Ireland), respectively. During the 20 minutes while awaiting test results, participants will complete an interviewer-administered survey (described below). If all 3 rapid tests are non-reactive, then the study visit will end after he or she has completed the questionnaire and received recruitment training and referral coupons. If any of the 3 rapid tests are reactive, then SSP staff will perform venipuncture to collect a blood specimen to be sent to the Wisconsin State Laboratory of Hygiene (WSLH) for confirmatory testing, record multiple methods of re-contacting the client, and arrange a follow-up visit to review confirmatory test results and provide linkage to care, if needed. In the event that a participant cannot provide a blood specimen for confirmatory testing due to poor venous access, they will be invited to return at a later date for another blood draw attempt. Those confirmed to have active HIV, HCV, or syphilis infection will be linked to a local provider with the assistance of a Vivent Health case manager.

**Laboratory-based confirmatory testing and specimen handling.** Specimens received by WSLH will be processed for confirmatory testing per standard protocols (see Facilities and Resources for details). After completing the required testing and reporting test results to the testing agency and the WI Surveillance System, WSLH staff will store plasma specimens in preparation for shipping to the CDC and/or GHOST laboratories, as described in Section 5.2

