Harmonization means the DCC will be combining similar data domains and questions across all sites in order to build large data sets that will be useful in answering questions that individual sites are not able to answer alone, either due to the nature of the question or sample size limitations. The University of Washington and other grantees will perform data analyses on these data for peer-reviewed publication. The harmonized datasets will be provided to other investigators funded under this study as required for analysis and will be considered under the umbrella of mandated DCC activities.

Upon execution of the agreement, the team’s data manager will upload study datasets to the Rural Opioid Initiative (ROI) Upload Server through a web interface. Access to the interface is controlled by usernames and passwords. Access is assigned to individual, designated ROI staff by the University

of Washington Data Coordinating Center (DCC). The web page uses the HTTPS protocol to transfer ROI data files securely to the Upload Server. HTTPS transfers are encrypted using Transport Layer Security (TLS, the successor to SSL), protecting the data en route to the server. The Upload Server is managed in accordance with the DCC's information security policies (<https://uwcirc.github.io/hipaa-policies>), and authorization for specific DCC staff is based on their project-related needs and responsibilities.

Data documentation will also be uploaded in the form of a data dictionary specifying all data elements within the dataset, including their description, valid values, and data type. Upon receipt of the dataset and documentation, the DCC data manager will work with the Wisconsin ROI data manager to understand the data structures so that the DCC may harmonize the dataset with those from other sites. A list of data elements that will be sent to the DCC is included in Appendix 3.

Table 6. Quantitative measures collected for Aim 1

Variable	Source	Measure/Operational Definition
Prevalence of HIV, HCV, , syphilis	Point-of-care screening + laboratory confirmation	Number of confirmed active cases / total number screened
Access to 9 prevention services	Participant questionnaire	Perceived accessibility using 5-pt Likert scales
Health insurance	Participant questionnaire	Access to Care Scale†59
Addiction severity	Participant questionnaire	Severity of Dependence Scale60
Barriers to care	Participant questionnaire	Kalichman's Barriers to Care Scale†61

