### 5.1.1 Additional Data Collection for DHS Linkage Study on COVID-19 Pandemic Impact Among UG3 Participants

We will use data collected by the Wisconsin Department of Health Services (DHS) to estimate the rates of COVID-19 infection, testing, hospitalization, and death, fatal and nonfatal drug overdoses, and vaccination against COVID-19, Hepatitis A and Hepatitis B in the UG3 cohort. To achieve our objectives, we propose a retrospective cohort study that will be facilitated by linking data from several DHS registries with UG3 participants. We propose to provide DHS colleagues with identifiable data from 991 of our prior research participants (identifiers: participant name, date of birth, gender, race, ethnicity, previous address, previous phone number, date of participation in our study) to facilitate linkage with several DHS registries. We are seeking approval for the DHS data linkage via a partial waiver of authorization, waiver of consent, and by maintaining a log of the protected health information provided to DHS per standardized disclosure logs (see here: <https://compliance.wisc.edu/wp-content/uploads/sites/102/2019/02/Accounting-for-Disclosures-Log-Research.pdf>). The linkage process is described below:

1. UW will provide a dataset containing a unique study identification number and participant name, date of birth, gender, race, ethnicity, previous address, previous phone number, and date of study participation to colleagues at DHS.

2. DHS will link identifiers with vital records data to identify the date (from study participation date through present day) and cause of any deaths that have occurred among participants of our prior study, from study participation date through present day.
3. DHS will link identifiers with COVID-19 data captured in WEDSS to identify the date of any COVID-19 tests, confirmed or probable infections, and hospitalizations.
4. DHS will link identifiers with WIR to identify the dates of all COVID-19 vaccination doses received and type of vaccine (brand or whether an mRNA/adenovirus vector vaccine).
5. DHS will link identifiers with WIR to identify the dates of all vaccine doses for hepatitis A or B received (including doses received before study participation, if possible).
6. DHS will link identifiers with hospitalization data to identify overdose events involving an emergency department visit or hospitalization.

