## 6.0 MEASUREMENT CONSIDERATIONS

### Data analysis for Aim 1.

The research questions under Aim 1 are descriptive rather than hypothesis-driven. The data collected for this Aim will be used in the UG3 phase to describe burden of infectious consequences of injection drug use, and self-reported access to essential prevention services in the selected rural communities. The same data will be used to establish baseline values in the pre/post analyses for the UH3 phase, if selected to proceed, described below (see Section 3.5.4). We will evaluate baseline statistics for participants recruited from the catchment areas associated with each Vivent Health prevention office, to determine if variation exists among rural regions of the state for each of the key variables of interest.

Prevalence estimates and standard errors will be calculated using RDSAT version 7.1. RDS accounts for a source of bias that is especially severe when sampling hard-to-reach groups; namely, that well-connected individuals tend to be over-sampled because many recruitment paths lead to them. RDS draws statistically valid samples of previously unreachable groups by keeping track of who recruited whom and their numbers of contacts eligible for recruitment. The recruitment process mathematical model weights the sample to compensate for non-random recruitment patterns. Based on Markov chain theory and biased network theory, the analysis provides unbiased population estimates and measures of the precision of the estimates.

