**HIV, HCV, and syphilis testing and counseling safeguards.** All testing staff have completed the Wisconsin AIDS/HIV Program state HIV test counselor training to ensure that HIV pre- and post-test counseling is conducted in accordance with state guidelines. Testing staff will be further required to complete training and demonstrate competence with the fingerstick collection of whole blood specimens (i.e., rapid HIV, HCV, and syphilis point-of-care testing methodology) and phlebotomy blood draws prior to study Implementation; and complete annual training in blood borne pathogen control ("universal precautions") to ensure adherence to the Occupational Safety and Health Administration Occupational Exposure to Blood borne Pathogen standards. Any new staff who are hired will be required to complete the training package described above, and demonstrate competency with HIV, HCV, and syphilis testing and counseling. [name]., will provide on-going review of counseling and testing procedures, as well as the interpretation and provision of test results to study participants. If any adverse physical harm results from the administration of the rapid HIV, HCV or syphilis tests, free medical follow-up will be provided to participants. Vivent Health is a CLIA-certified HIV test site funded, in part, by the Wisconsin Division of AIDS/HIV's HIV testing program.

Specimens will only be sent for confirmatory testing for those rapid tests that they are already positive for, therefore, no new health information will be generated by analysis of these samples.

**COVID-19 Pilot.** All data collected from participants will be stored on a secure server, REDCap, Qualtrics, and/or Client Point. Participants will be assigned a unique study ID, which will be linked to their name in on the screening form, housed on the Vivent Health server, PHI box, and REDCap. All other forms used for these participants will only have their study ID attached. Testing forms will follow Vivent Health's virtual testing protocol.

All calls for virtual navigation, and originally proposed UH3 navigation performed virtually, will be conducted through a cell phone provided by UW or Vivent Health, or on Vivent Health's approved video conferencing platform, Microsoft teams. Staff may conduct reminders or follow ups via their work telephone. Facebook messenger from a business profile, or mail if the client consents to that form of contact.

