## **L. Incentives**

**Aim 1 and 2.** Participants will receive \$20 remuneration for survey participation on the day of enrollment, and will receive a smaller incentive of \$10 for each eligible peer recruit who enrolls in the study. For participants who have a reactive HCV rapid test and are unable to provide a blood sample for HCV confirmatory testing due to phlebotomy difficulties, a one-time incentive of \$10 will be provided if they return at a later date and attempt a second blood draw. Syringe program clients and local service providers who agree to participate in qualitative interviews will be paid an incentive of

\$30 each for one hour-long interview. All primary care providers who are selected to participate in the quantitative mail-based survey will receive an incentive of \$5 at the time the survey is mailed to them.

**Aim 3.** Participants will receive \$20 remuneration for survey participation and rapid testing on the day of enrollment, and will receive an additional incentive of \$20 for 3-month, and 6-month assessments. Participants may also receive a monthly incentive of \$5 to update their contact information so we have the most up to date information to decrease the risk of loss to follow up if it is deemed necessary to do so. For participants who have a reactive HCV rapid test and are unable to provide a blood sample for HCV confirmatory testing due to phlebotomy difficulties, a one-time incentive of \$10 will be provided if they return at a later date and attempt a second blood draw. Additionally, participants will receive \$10 for each eligible peer recruit who enrolls in the study.

**COVID-19 Pilot.** Participants will receive \$10 for each research assessment (baseline, 4 weeks, and 30-days post service resumption). There will be no incentives for testing during this sub-phase of the study.

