HIV DIAGNOSIS AND TREATMENT (HHIHIV SERIES)	Questions on whether participant has been tested for HIV, last HIV test date, test results, date of diagnosis, HIV treatment
HCV DIAGNOSIS AND TREATMENT (HHIHCV SERIES)	Questions on HCV diagnosis, treatment for HCV, and main place for medical care for HCV
BACTERIAL INFECTIONS	Hospitalization of serious bacterial infection, date of hospitalization
ACCESS TO MEDICAL CARE	Main place participant received medical care, barriers to care

KESSLER DISTRESS SCALE (KES SERIES)	Questions on participants anxiety and depressive symptoms in the last 30 days
PTSD SCALE	Questions on whether participant experienced adverse event, and symptoms experienced after adverse event
ACCESS TO PREVENTION AND TREATMENT (ACC SERIES)	Questions on accessibility to condoms, HIV treatment, HCV treatment, STI treatment, buprenorphine, naloxone, clean syringes, vaccinations, infection information
CRIMINAL JUSTICE	Times law enforcement has stopped and searched participant, number of arrests, probation in the last 6 months, days they were in jail
SEXUAL RISK (SXR SERIES)	Number of partners in the past 30 days, trade sex for drugs, last time they had vaginal or anal sex, sex without a condom, sex without a condom and injected drugs, sex with HIV+
DEMOGRAPHICS	Main source of income, services received, relationship status, student status, pregnancy status, forms of birth control, homelessness, transportation, health insurance
RDS	Questions on their network of people who inject drugs
RAPID RESULTS	Results from HIV, HCV, and Syphilis testing that was done that day
DUP_ID	Possible participants that entered the study more than once
Qualitative Participant Interviews	
All transcripts were stripped of the following information:	Names Geographic subdivisions smaller than a state All Dates Telephone numbers FAX numbers Email addresses Social security numbers Medical record numbers Health plan number Account number Certificate/license number License plate number Device identifiers/serial numbers Web urls Internet protocol addresses Biometric identifiers Full face photos and comparable images

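### Table 6 counts reactive participants with no confirmatory result as non-cases, so the Aim 1 HCV prevalence sits at its lower bound; the size of the shortfall is unknown and may be small

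*Combined protocol and SAP*

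**What the plan says.** Section 5.1 sends a participant to venipuncture only after a reactive rapid test. Section 9.0 H agrees: "Specimens will only be sent for confirmatory testing for those rapid tests that they are already positive for". The rapid HCV test detects antibody, and Section 5.1 describes HCV confirmation as RNA testing, so a reactive HCV result alone does not establish active infection. Table 6 then gives one operational definition for HIV, HCV and syphilis: "Number of confirmed active cases / total number screened".

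The protocol expects some confirmations to fail. Section 5.1 begins one provision "In the event that a participant cannot provide a blood specimen for confirmatory testing due to poor venous access" and invites the participant back for another attempt. Section 9.0 L pays a one-time incentive for a second attempt to those "unable to provide a blood sample for HCV confirmatory testing due to phlebotomy difficulties". Staff are also to "record multiple methods of re-contacting the client, and arrange a follow-up visit to review confirmatory test results".

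The Aim 1 analysis in Section 6.0 specifies RDSAT weighting and standard errors. Neither it nor Table 6 says how to classify a reactive participant who never obtains a confirmatory result. The instruction in Section 9.0 D to treat a lost assessment as missing concerns Aim 3.

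**The concern.** A participant with a reactive rapid test and no confirmatory result has unknown status. The Table 6 ratio resolves that unknown one way only: the person is counted as screened and cannot be counted as a case. For HCV this amounts to assuming that none of them is actively infected, which nothing in the documents supports. RDS weights correct for unequal recruitment and leave this coding untouched. Because the weights are positive, they do not change the direction either.

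Prevalence of these infections is the stated estimate of Aim 1 and is to be described by catchment area. A standard error computed from the ratio reflects sampling variation only, so the reported interval would not show the error.

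**Working it through.** **Inputs from the documents.** The ratio is from Table 6 and the testing sequence from Section 5.1. The number screened is taken as 991, from Section 5.1.1 ("identifiable data from 991 of our prior research participants"); the planned enrolment in Section 4.0 was 1,200. The design effect is 2, the upper value in Section 7.0. The documents state no prevalence, reactive share or unconfirmed share, so there is no figure of the plan's own to reproduce.

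**Assumed inputs.** r = share reactive; u = share of reactives without a confirmatory result; a1 = share active among confirmed reactives; a0 = share active among unconfirmed reactives.

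**Bias.**
- True active prevalence = r × [(1 − u) × a1 + u × a0]
- Table 6 value q = r × (1 − u) × a1
- Difference = −r × u × a0

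The difference is zero if a0 = 0 and negative otherwise. From this source the ratio cannot err upward.

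**Coverage.** SE = √(2 × q × (1 − q) / n), z = bias / SE, coverage of a nominal 95% interval = Φ(1.96 − z) − Φ(−1.96 − z). Example at r = 0.50, a0 = a1 = 0.70, u = 10%: true value 35.0%, q = 0.50 × 0.90 × 0.70 = 31.5%, SE = √(2 × 0.315 × 0.685 / 991) = 0.0209, z = 0.035 / 0.0209 = 1.68, coverage 61%.

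HCV, r = 0.50, a0 = a1 = 0.70, n = 991:

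| u | Table 6 value | Bias (points) | Coverage |
|---|---|---|---|
| 1% | 34.65% | 0.35 | 95% |
| 2% | 34.3% | 0.7 | 94% |
| 5% | 33.25% | 1.75 | 87% |
| 10% | 31.5% | 3.5 | 61% |
| 20% | 28.0% | 7.0 | 7% |

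Over the same u values, r = 0.30 gives coverage of 95 / 94 / 91 / 78 / 29%, and r = 0.70 gives 94 / 93 / 81 / 41 / 1%. At r = 0.50, u = 10% and a1 = 0.70, moving a0 from 0.5 to 0.9 moves the bias from 2.5 to 4.5 points.

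**When bias exceeds sampling error.** With full confirmation at r = 0.50 the half-width is 1.96 × √(2 × 0.35 × 0.65 / 991) = 4.2 points. The bias passes that only above u = 4.2 / 35 = 12%.

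**Single site.** 991 / 6 is about 165. At r = 0.50 the half-width is 10.3 points and coverage is 94 / 89 / 71% at u = 5 / 10 / 20%. Noise dominates unless u is large.

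**HIV and syphilis.** The bias cannot exceed r × u. At an assumed 2% reactive and u = 20% that is 0.02 × 0.20 = 0.4 points. A site of 165 would have 0.02 × 165 = 3.3 reactives.

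**Bounds for HCV at r = 0.50.** The range runs from q (all unconfirmed inactive) to q + r × u (all active): 31.5 to 36.5% at u = 10%, 28.0 to 38.0% at u = 20%. Table 6 always reports the lower end.

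**Dropping the unconfirmed does not cure it.** They are all reactive, so removing them removes high-risk people. At r = 0.50, u = 10%, a0 = a1 = 0.70 the result is 0.315 / 0.95 = 33.2%, against a true 35.0%.

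**The case against.** Table 6 is a one-line measure in the data-collection section, not a missing-data rule, and an analyst might treat an incomplete screen-and-confirm sequence as indeterminate. That is possible, but the line names both numerator and denominator, and no other text overrides it. Following it as written gives the biased figure.

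The protections in Sections 5.1 and 9.0 L are real. Venipuncture follows the reactive test directly, and re-contact, a repeat draw and payment for HCV should keep u low. This stands, and it limits what can be said about size. The low coverage figures belong to u of 10% or more, which the documents give no reason to expect.

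Aim 1 is descriptive ("The research questions under Aim 1 are descriptive rather than hypothesis-driven") and its survey phase ran to August 2019, so the request now concerns analysis and reporting. This also stands and lowers the severity.

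The alternative estimator has weaknesses. It assumes confirmation is missing at random among reactives; if that fails, an error of r × u × (a1 − a0) remains. On bias alone it is worse than Table 6 only when a0 is below half of a1. On mean squared error the break-even is a0 = [a1² + (Vp − Vt) / (r × u)²] / (2 × a1), where Vp and Vt are the variances of the product and of the Table 6 ratio. At n = 165, r = 0.50 and a1 = 0.70 this is about 0.50 at u = 5% and 0.43 at u = 10%, not 0.35. Confirmed reactives are also a subset cut out of the recruitment chains, and the documents do not show that RDSAT performs well there. These points argue for imputing within the full sample and for showing the bounds. They do not rescue a rule that sets a0 to zero.

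**Conclusion.** The point holds in limited form. Applied literally, the Table 6 ratio places HCV prevalence at its lower bound with respect to unconfirmed reactives, and biases it down by r × u × a0 if any of them is actively infected. The direction follows from the text. The size does not: r, u, a0 and a1 are all assumed here, and 991 is taken as the number screened. At u of 1 to 2% and r of 0.30 to 0.70 coverage stays at 93 to 95%; at r = 0.50 and u = 10% it falls to about 61%. The effect falls on the pooled HCV estimate.

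Two stronger readings are tempting. One is that Aim 1 HCV prevalence is materially understated. The documents do not support this, because they give no value of u and describe steps that should hold it down. The other is that site selection or the UH3 evaluation is compromised. The progression milestones in Section 6.0 do not use prevalence, Section 4.0 already names the sites, Section 5.4 gives Aim 3 its own baseline, and Appendix 2 takes HCV and HIV prevalence from the state surveillance system.

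Section 6.0 does, however, say that the Aim 1 data will supply baseline values for the UH3 pre/post analyses, and its triangulation paragraph feeds prevalence into the evaluation of counties. Those statements and Section 5.4 should be reconciled, so that the use of this estimate is clear. Severity: minor to moderate.

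**What to change.** In Table 6, stop counting unconfirmed reactives as non-cases in the HCV estimate.

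- **All three infections:** report the rapid-reactive proportion (antibody, for HCV), the number of unconfirmed reactives by site, and prevalence under both bounds: all unconfirmed inactive (the present formula) and all active.
- **HCV point estimate:** assign unconfirmed reactives the active share seen among confirmed reactives. Use either the weighted reactive proportion times the weighted active proportion, or equivalent imputation within the full RDS sample. State the missing-at-random assumption and take the interval from a bootstrap that keeps the recruitment chains intact.
- **HIV and syphilis:** keep the present ratio, with the bounds. With about 3 reactives per site at an assumed 2% reactive, the product would be unstable.
- **Use of the estimate:** reconcile Section 6.0 with Section 5.4 on which data form the UH3 baseline.

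No new data are needed. Confirmatory results are already collected, and Appendix 3 lists "Results from HIV, HCV, and Syphilis testing that was done that day", so unconfirmed reactives can be identified. The HCV interval widens a little: at r = 0.50, a1 = 0.70, n = 991, with a design effect of 2 and no covariance between the factors, the product variance is 2r(1 − r)a1²/n + 2r × a1(1 − a1)/[n(1 − u)]. The half-width goes from 4.1 to 4.3 points at u = 10% and from 4.0 to 4.4 at u = 20%. The other cost is reliance on missing at random, which the bounds make visible.
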